- l If an *ad hoc* visit occurs in combination with a planned visit, blood sampling will only be ≤120 mL for T-cell and B-cell response assessments and one 20 mL sample for serological testing for SARS-CoV-2 N-binding antibodies and humoral immunogenicity assessments.
- m One-year FU (386±10 days) will only apply for subjects who for any reason do not receive the third IMP injection.

- n ~15 subjects at preselected sites in Part B will be evaluated in terms of cell-mediated immunity.
- o For any visits >1 month after each IMP injection, only prohibited medications should be recorded.

Abbreviations: AE = adverse event; AESI = AE of special interest; ECG = electrocardiogram; e-diary = electronic diary or an equivalent application; EOT = end of trial; FU = follow-up; h = hour(s); IMP = investigational medicinal product; mon = month(s); N-binding = nucleocapsid-binding; NAAT = nucleic acid amplification-based test; SAE = serious AE; SARS-CoV-2 = the virus leading to COVID-19; SoA = schedule of activities; Vax = vaccination (i.e., IMP injection); wk = week(s); WOCBP = women of childbearing potential; yr = year(s).

**Table 6: Schedule of events for Part C, Cohorts 7 and 8; one dose of BNT162b2 (B.1.1.529) or BNT162b2 in subjects who received two or three doses of any COVID-19 RNA-based vaccine prior to a SARS-CoV-2 infection from January 2022 onwards**

Activity	Visit 0	Visit 1	Visit 2	Visit 3	Visit 4	Visit 5	Visit 6/ EOT	Early termination	COVID-19
Visit description	Screening	Pre-Vax (except IMP injection)	1 wk Post-Vax FU	1 mon Post-Vax FU	3 mon Post-Vax FU	6 mon Post-Vax FU	1 yr Post-Vax FU		Ad hoc
Day (relative to Visit 1 on Day 1)	-7 to -1	1	8+2	29±3	85±5	180±10	360±10		
Collect informed consent	X								
Assess inclusion/exclusion criteria compliance	X	X (review)							
Collect demographic and medical history	X	X (update)							
12-lead ECG	X	X g	X						
Perform physical examination (incl. body weight) and vital signs a	X	X							
Blood (15 mL) and urine collection for clinical assessments	X								
Record (concomitant) medication l	X	X	X	X	X m	X m	X m	X m	X m
Perform urine pregnancy test for WOCBP	X	X							
Oral swabs for NAAT-based SARS-CoV-2 for screening	X	X b							
Randomization		X							
IMP injection and assess acute reactions for ≥30 minutes after IMP injection		X							
Measure oral body temperature		X c	X	X					
Issue/train and collect e-diary		Issue/train	Collect					Collect	

Activity	Visit 0	Visit 1	Visit 2	Visit 3	Visit 4	Visit 5	Visit 6/ EOT	Early termination	COVID-19
Visit description	Screening	Pre-Vax (except IMP injection)	1 wk Post-Vax FU	1 mon Post-Vax FU	3 mon Post-Vax FU	6 mon Post-Vax FU	1 yr Post-Vax FU		Ad hoc
Day (relative to Visit 1 on Day 1)	-7 to -1	1	8+2	29±3	85±5	180±10	360±10		
Subjects report daily reactivity (incl. oral body temperature) for 7 days after dosing using an e-diary		Start after Vax	End						
Review e-diary data		Start	End						
Record any AEs, AESIs, or SAEs since last visit h		X	X	X	X e	X e	X e	X e	X e
Oral swabs for NAAT-based SARS-CoV-2 for surveillance			X	X	X	X	X	X	X
Oral swabs for SARS-CoV-2 sequencing d	X	X	X	X	X	X	X	X	X
Blood draws for serological testing for SARS-CoV-2 N-binding antibodies and for humoral immunogenicity assessments (30 mL) f		X	X	X	X	X	X	X	X j
SARS-CoV-2 N-binding antibodies assessment (5 mL) n	X								
Blood draws for T- and B-cell responses (135 mL) i		X	X	X	X	X	X		X j
Blood draw for HLA		X k							
Record pregnancies		Start	=>	=>	=>	=>	End	End	

Note: The SoA allows for *ad hoc* visits for SARS-CoV-2 testing for symptomatic or asymptomatic subjects.

a At Visit 0: complete physical examination including body weight and vital signs (oral body temperature, heart rate, blood pressure [systolic and diastolic]); at Visit 1: symptom-orientated physical examination.

- b If the result from an oral swab for NAAT-based SARS-CoV-2 is not older than 24 h at the planned time of IMP injection, availability of the test result from Visit 1 on Day 1 is optional.
- c Issue thermometer or other measuring device for subjects to measure their oral body temperature each day and if they experience flu-like symptoms.
- d All swabs will be analyzed, even if no COVID-19 symptoms are shown.
- e For any visits >1 month after each IMP injection, only IMP-related AEs, trial procedure-related AEs, AESIs, any SAEs. In addition, all AEs linked to confirmed COVID-19 cases will be recorded.
- f Blood samples will be stored and may be analyzed retrospectively for additional clinical parameters (troponin, cytokine).
- g The 12-lead ECG at Visit 1 can be skipped if the 12-lead ECG from Visit 0 was performed within 24 h prior to the planned IMP dose.
- h The recording will start from IMP allocation during Visit 1 (after eligibility is confirmed).
- i Biomarker/PBMC subgroup (~25 subjects in each cohort).
- j If an *ad hoc* visit occurs in combination with a planned visit, blood sampling will only be ≤135 mL for T-cell and B-cell response assessments and one 30 mL sample for serological testing for SARS-CoV-2 N-binding antibodies and humoral immunogenicity assessments.
- k A 5 mL blood sample will be taken for genetics (HLA typing) within the biomarker/PBMC subgroup (~25 subjects in each cohort).
- l Subjects who receive non-trial SARS-CoV-2 vaccinations will be discontinued, resulting in an early termination visit. For subjects who receive non-trial SARS-CoV-2 vaccinations, there will be no blood sampling for humoral immunogenicity or T-cell and B-cell response assessments at the early termination visit.
- m For any visits >1 month after each IMP injection, only prohibited medications should be recorded.
- n SARS-CoV-2 N-binding antibodies assessment only to be done by local lab when no historic NAAT result is available to prove prior SARS-CoV-2 infection.

Abbreviations: AE = adverse event; AESI = AE of special interest; ECG = electrocardiogram; e-diary = electronic diary or an equivalent application; EOT = end of trial; FU = follow-up; h = hour(s); HLA = human leukocyte antigen; IMP = investigational medicinal product; mon = month(s); N-binding = nucleocapsid-binding; NAAT = nucleic acid amplification-based test; PBMC = peripheral blood mononuclear cell; SAE = serious AE; SARS-CoV-2 = the virus leading to COVID-19; SoA = schedule of activities; Vax = vaccination (i.e., IMP injection); wk = week(s); WOCBP = women of childbearing potential; yr = year(s).

**Table 7: Schedule of events for Part C, Cohort 9; no vaccination (within 3-month period) in subjects who received two or three doses of any COVID-19 RNA-based vaccine prior to a SARS-CoV-2 infection from January 2022 onwards**

Activity	Visit 0	Visit 1	Visit 2	Visit 3	Visit 4/ EOT	Early termination	COVID-19
Visit description	Screening	Day 1	1 wk	1 mon	3 mon		Ad hoc
Day (relative to Visit 1 on Day 1)	-7 to -1	1	8+2	29±3	85±5		
Collect informed consent	X						
Assess inclusion/exclusion criteria compliance	X	X (review)					
Collect demographic and medical history	X	X (update)					
12-lead ECG	X	X g					
Perform physical examination (incl. body weight) and vital signs a	X	X					
Blood (15 mL) and urine collection for clinical assessments	X						
Record (concomitant) medication e	X	X	X	X	X m	X m	X m
Perform urine pregnancy test for WOCBP	X	X					
Oral swabs for NAAT-based SARS-CoV-2 for screening	X	X b					
Randomization		X					
Measure oral body temperature		X c	X	X			
Oral swabs for NAAT-based SARS-CoV-2 for surveillance			X	X	X	X	X
Oral swabs for SARS-CoV-2 sequencing d	X	X	X	X	X	X	X
Record any AEs, AESIs, or SAEs since last visit h		X	X	X	X l	X l	X l
SARS-CoV-2 N-binding antibodies assessment (5 mL) b	X						
Blood draws for serological testing for SARS-CoV-2 N-binding antibodies and for humoral immunogenicity assessments (30 mL) f		X	X	X	X		
Blood draws for T- and B-cell responses (135 mL) i		X	X	X	X		X j
Blood draw for HLA		X k					
Record pregnancies		Start	=>	=>	End	End	

Note: The SoA allows for *ad hoc* visits for SARS-CoV-2 testing for symptomatic or asymptomatic subjects.

- a At Visit 0: complete physical examination including body weight and vital signs (oral body temperature, heart rate, blood pressure [systolic and diastolic]); at Visit 1: symptom-orientated physical examination.
- b SARS-CoV-2 N-binding antibodies assessment only to be done by local lab when no historic NAAT result is available to prove prior SARS-CoV-2 infection.
- c Issue thermometer or other measuring device for subjects to measure their oral body temperature each day and if they experience flu-like symptoms.
- d All swabs will be analyzed, even if no COVID-19 symptoms are shown.
- e Subjects who receive non-trial SARS-CoV-2 vaccinations will be discontinued, resulting in an early termination visit. For subjects who receive non-trial SARS-CoV-2 vaccinations, there will be no blood sampling for humoral immunogenicity or T-cell and B-cell response assessments at the early termination visit.
- f Blood samples will be stored and may be analyzed retrospectively for additional clinical parameters (troponin, cytokine).
- g The 12-lead ECG at Visit 1 can be skipped if the 12-lead ECG from Visit 0 was performed within 24 h of Visit 1.
- h The recording will start during Visit 1 (after eligibility is confirmed).
- i Biomarker/PBMC subgroup (~25 subjects).
- j If an *ad hoc* visit occurs in combination with a planned visit, blood sampling will only be ≤135 mL for T-cell and B-cell response assessments.
- k A 5 mL blood sample will be taken for genetics (HLA typing) within the biomarker/PBMC subgroup (~25 subjects).
- l For any visits >1 month after Visit 1, only trial procedure-related AEs, AESIs, any SAEs. In addition, all AEs linked to confirmed COVID-19 cases will be recorded.
- m For any visits >1 month after Visit 1, only prohibited medications should be recorded.

Abbreviations: AE = adverse event; AESI = AE of special interest; ECG = electrocardiogram; EOT = end of trial; h = hour(s); mon = month(s); HLA = human leukocyte antigen; N-binding = nucleocapsid-binding; NAAT = nucleic acid amplification-based test; PBMC = peripheral blood mononuclear cell; SAE = serious AE; SARS-CoV-2 = the virus leading to COVID-19; SoA = schedule of activities; wk = week(s); WOCBP = women of childbearing potential.

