## Objectives and endpoints

### Objectives and endpoints - Part A

OBJECTIVES	ESTIMANDS	ENDPOINTS
Primary objectives (Safety)		

To describe the safety profile of the multivalent vaccine BNT162b2 (B.1.1.7 + B.1.617.2), given as one or two booster doses to BNT162b2-experienced subjects, or as three doses to COVID-19 vaccine-naïve subjects.
 
To describe the safety profile of the monovalent vaccine BNT162b2 (B.1.1.7) given as one booster dose to BNT162b2-experienced subjects. *
 
To describe the safety profile of the monovalent vaccine BNT162b2 (B.1.617.2), given as one booster dose to BNT162b2-experienced subjects. *
 
To describe the safety profile of BNT162b2, given as one booster dose to BNT162b2-experienced subjects. *
	
For each trial treatment, in subjects receiving at least one dose of IMP, the percentage of subjects reporting:
 
 
• Local reactions at the injection site up to 7 days after each dose.
 
• Systemic events up to 7 days after each dose.
 
• AEs from Dose 1 up to 1 month after each dose.
 
• SAEs from Dose 1 up to 6 months after the last dose.
 
	
 
• Local reactions (pain, tenderness, erythema/redness, induration/swelling)
 
• Systemic events (fever, fatigue, headache, chills, vomiting, nausea, diarrhea, new or worsened muscle pain, and new or worsened joint pain)
 
• AEs
 
• SAEs
 

Secondary objectives (Immunogenicity)		

To describe the immune response after one, two, or three doses of BNT162b2 (B.1.1.7 + B.1.617.2), BNT162b2 (B.1.1.7), BNT162b2 (B.1.617.2), and BNT162b2.
	
For BNT162b2-experienced subjects:
 
 
• GMTs at each time point.
 
• GMFR from before vaccination to each subsequent time point after vaccination.
 
• Seropositivity (SR) in terms of NT at each post-vaccination time point.
 
	
 
• Reference and VOC specific NTs
 

OBJECTIVES	ESTIMANDS	ENDPOINTS
Exploratory objectives		

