Blood draws for serological testing for SARS-CoV-2 N-binding antibodies and for humoral immunogenicity assessments (20 mL)		X	X	X	X	X	X	X	X i
Blood draws for T- and B-cell responses (120 mL)		X	X		X e	X	X		X i
Blood draw for explorative research (25 mL) k				X					
Record pregnancies		Start	=>	=>	=>	=>	End	End	

Notes: The SoA allows for *ad hoc* visits for SARS-CoV-2 testing for symptomatic or asymptomatic subjects. "BNT162b2-experienced" is defined as subjects who have previously received two injections of 30 µg BNT162b2.

- a At Visit 0: complete physical examination including body weight, vital signs (oral body temperature, heart rate, blood pressure [systolic and diastolic]), blood and urine clinical laboratory tests; at Visit 1: symptom-orientated physical examination.
- b If the result from an oral swab for NAAT-based SARS-CoV-2 is not older than 24 h at the planned time of IMP injection, availability of the test result from Visit 1 on Day 1 is optional.
- c Issue thermometer or other measuring device for subjects to measure their oral body temperature each day and if they experience flu-like symptoms.
- d All swabs will be analyzed, even if no COVID-19 symptoms are shown.
- e 5 mL blood will be taken from this sample for genetics (human leukocyte antigen typing).
- f For any visits >1 month after IMP injection, only IMP-related AEs, trial procedure-related AEs, AESIs, any SAEs. In addition, all AEs linked to confirmed COVID-19 cases will be recorded.
- g The 12-lead ECG at Visit 1 can be skipped if the 12-lead ECG from Visit 0 was performed within 24 h prior to the planned IMP dose.
- h For subjects rolling over from the trial BNT162-02 / C4591001 (NCT04368728), the recording will start from IMP allocation during Visit 1 (after eligibility is confirmed and the subject is withdrawn from the trial BNT162-02 / C4591001).

- i If an *ad hoc* visit occurs in combination with a planned visit, blood sampling will only be ≤120 mL for T-cell and B-cell response assessments and one 20 mL sample for serological testing for SARS-CoV-2 N-binding antibodies and humoral immunogenicity assessments.
- j Subjects who receive non-trial SARS-CoV-2 vaccinations will be discontinued, resulting in an early termination visit. For subjects who receive non-trial SARS-CoV-2 vaccinations, there will be no blood sampling for humoral immunogenicity or T-cell and B-cell response assessments at the early termination visit.

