## **7.2 Trial subject discontinuation or withdrawal from the trial**

A trial subject may withdraw from the trial at any time at his/her own request or may be discontinued from the trial at any time at the discretion of the investigator for safety, behavioral, compliance, or administrative reasons. Withdrawals are expected to be uncommon.

Reasons for discontinuation from the trial include the following:

- Refused further trial procedures
- Lost to follow-up
- Death
- Trial terminated by sponsor
- Trial subject request
- Investigator request
- Important protocol deviation per the investigator after consultation with the Medical Monitor
- Receipt of non-trial SARS-CoV-2 vaccination during the trial

If the trial subject withdraws consent for data processing, the sponsor may retain and continue to use any data collected before such a withdrawal of consent.

For trial subjects who withdraw consent, the investigator must clarify whether consent for research sample storage/processing (if given) is also withdrawn. If yes, then they must be informed that any research samples collected will be destroyed. The investigator must document research sample destruction in the Investigator's Site File (ISF) and inform the sponsor about the withdrawal of consent immediately.

If possible, permanently discontinued trial subjects will complete all assessments planned for the Early Termination Visit.

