### **8.3.1 Time period and frequency for collection of AE, AESI, and SAE information**

All AEs, AESI, and SAEs (including a death) will be recorded at the time points listed in the SoA in Section 1.3.

For subjects who receive a non-trial SARS-CoV-2 vaccination, AEs/SAEs will be collected as specified above until the date when the subject was vaccinated with the non-trial SARS-CoV-2 vaccine. The AEs/SAEs expected to be captured after non-trial SARS-CoV-2 vaccination are within the frame of post-marketing safety data reporting.

Cohort 9 subjects will be offered a booster vaccination with the locally marketed Pfizer-BioNTech RNA-based COVID-19 vaccine after the EOT has been completed. If subjects choose to receive this vaccination, the recording and follow-up of any safety events will

follow post-marketing rules and such events will not be recorded within the trial documentation.

Investigators are not obligated to actively seek AEs or SAEs at any time after a trial subject has been discharged from the trial, however, if the investigator learns of any SAE (including a death), that they consider to be reasonably related to the IMP administration or trial participation, the investigator must promptly notify the sponsor.

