#### **10.3.1.10 Reporting of SAEs and AESIs**

All SAEs and AESIs (even if non-serious) which occur in a trial subject during the observation period, whether considered to be associated with trial medication or not, must be reported by the investigator to the sponsor within 24 h following knowledge of the event.

All SAEs occurring after the end of the observation period only have to be reported to the sponsor if the investigator suspects a relationship to trial medication or the trial procedure.

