5.2.1 Analyses for binary data

Descriptive statistics for categorical variables (e.g., proportions) are the percentage (%), with the number of subjects with data on the specified characteristic as the numerator (n), and the number of subjects in the specific analysis set as denominator (N) used in the percentage calculation, and the 95% CIs where applicable.

The exact 95% CI for binary endpoints for each group will be computed using the F distribution (Clopper-Pearson; [Agresti 2002](#)). Unless otherwise stated, the 95% CI for the between-group difference for binary endpoints will be calculated using the Miettinen and Nurminen method ([Miettinen and Nurminen 1985](#)).

For between-group comparison of SR, the difference will be estimated using minimum risk weights and stratified by sex and age group (18 to 55 years, 56 to 85 years). The associated 95% CI will be calculated using stratified Newcombe confidence interval weighted with minimum risk to combine the stratum components and continuity correction.

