6.1.1.5 Serious adverse events

The number of events, number and percentage of subjects reporting serious TEAEs and serious related TEAEs up to 6 months after last dose will be summarized in the same manner as the AEs. The non-serious AEs will also be summarized.

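### The primary SAE percentage counts subjects who leave after a non-trial COVID-19 vaccine as non-events for the whole window, so it understates the full-window risk by an unknown, probably small, amount.

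*Protocol*

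**What the plan says.** **Leaving the trial.** The notes to the schedule-of-activities tables in Protocol 1.3 state that "Subjects who receive non-trial SARS-CoV-2 vaccinations will be discontinued, resulting in an early termination visit". Protocol 7.2 lists "Receipt of non-trial SARS-CoV-2 vaccination during the trial" among the reasons for discontinuation and expects withdrawals to be uncommon.

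**SAE collection.** Protocol 8.3.1 says that for these subjects "AEs/SAEs will be collected as specified above until the date when the subject was vaccinated with the non-trial SARS-CoV-2 vaccine", and assigns later events to post-marketing reporting. Protocol 10.3.1.10 adds: "All SAEs occurring after the end of the observation period only have to be reported to the sponsor if the investigator suspects a relationship".

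**The endpoint.** In all three parts the primary safety estimand is the percentage of subjects with at least one dose who report "SAEs from Dose 1 up to 6 months after the last dose".

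**The analysis.** SAP 6.1.1.5 says that serious TEAEs "up to 6 months after last dose will be summarized in the same manner as the AEs", that is, as number of events and number and percentage of subjects. SAP 5.2.1 sets "the number of subjects in the specific analysis set as denominator (N) used in the percentage calculation". SAP 6.1.1 uses the Safety Set, meaning everyone dosed, and bases post-Dose 2 and post-Dose 3 summaries on subjects who received those doses. SAP 5.3 imputes nothing except partial dates. The only SAP rule on data after a non-trial vaccine, in 5.2, concerns immunogenicity.

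**The concern.** Observation and denominator do not match. The window is fixed by the endpoint definition, but the protocol cuts observation short for a defined group, and that group stays in the denominator. A subject seen for 2 of 6 months without an SAE contributes exactly what a subject seen for all 6 months does. The plan states no intercurrent-event strategy, censoring rule or exposure adjustment for SAEs.

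This is a primary safety endpoint, and the error runs in the reassuring direction. The planned outputs would not let a reader gauge it: the disposition table in SAP 6.5.2.1 splits withdrawals only at the visit 1 month after the last dose, so it does not show how many subjects were followed through the 6-month SAE window. Yet SAP 5.2.2 already defines a person-years rate with an exact Poisson interval, and 6.3 applies it to exploratory endpoints (confirmed COVID-19 and N-binding seroconversion).

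**Working it through.** The documents give no expected SAE risk and no expected rate of non-trial vaccination, so there is no figure of the plan to reproduce. What follows is an illustration over stated assumptions.

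**Inputs**
- n = 375 enrolled per Part B cohort (Protocol 9.2.2).
- p = true SAE risk over the full window: assumed, 1% or 2%.
- q = share leaving inside the window: assumed, 5%, 10% or 30%.
- u = fraction of the window observed in those who leave: 0.5 on average if they leave evenly.
- Constant hazard, and leaving unrelated to SAE risk.

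**Formula.** With h = -ln(1 - p) measured per window,

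crude percentage = (1 - q) × p + q × (1 - exp(-h × u)).

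For small p, 1 - exp(-h × u) is close to p × u. The crude percentage is then about p × [1 - q × (1 - u)], which is p × (1 - q/2) at u = 0.5. The relative shortfall is about q/2, almost regardless of p.

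**Worked case.** At p = 1%, h = 0.01005 and the risk over half the window is 1 - exp(-0.005025) = 0.501%. For q = 10%: 0.90 × 1% + 0.10 × 0.501% = 0.950%. For q = 30%: 0.70 × 1% + 0.30 × 0.501% = 0.850%.

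| p | q | Crude % (u = 0.5) | Relative shortfall | Expected subjects with an SAE, n = 375 |
|---|---|---|---|---|
| 1% | 5% | 0.975 | 2.5% | 3.66 vs 3.75 |
| 1% | 10% | 0.950 | 5.0% | 3.56 vs 3.75 |
| 1% | 30% | 0.850 | 15.0% | 3.19 vs 3.75 |
| 2% | 10% | 1.901 | 5.0% | 7.13 vs 7.50 |
| 2% | 30% | 1.702 | 14.9% | 6.38 vs 7.50 |

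The last column sets the crude expectation against n × p with full follow-up.

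**Sensitivity to timing.** At p = 1% and q = 30%, moving u from 0.25 to 0.75 moves the crude percentage from 0.775% to 0.925%.

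Only leaving inside the SAE window matters. One-dose subjects have visits to Day 360, but the SAE window closes at about Day 180, so later departures have no effect. The same arithmetic applies to any early withdrawal; non-trial vaccination is the case that the protocol itself imposes.

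**The case against.** The strongest reply is that little depends on this. Safety objectives are descriptive, and hypotheses are tested only on Part B immunogenicity. Withdrawals are expected to be uncommon, and Protocol 6.5.2 says subjects should not take a non-trial vaccine. The shift is also small beside sampling error: for 8 of 375 subjects (2.1%) the exact 95% interval is about 0.9% to 4.2%, while the assumed cases above move the expected count by about one subject or less (7.50 - 6.38 = 1.12 at most). The cut-off has a rationale too, since events after another COVID-19 vaccine are confounded by it. All of this stands and limits the size of the point. It does not answer the mismatch between observation and denominator.

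Three stronger readings are tempting, but the documents do not support them.
- **That all later SAEs are lost.** SAEs are recorded at the early termination visit, and a later SAE judged related is still reportable if the investigator learns of it (Protocol 8.3.1 and 10.3.1.10). The documents do not say whether such an event would enter the endpoint.
- **That SAE percentages cannot be compared across cohorts.** No such comparison is planned. The longer window in Cohort 6 follows from the endpoint definition and would exist with no dropout. A bias that differs by cohort would need different leaving rates or times, for which there are no figures.
- **That every percentage divides by the whole Safety Set.** SAP 6.1.1 limits post-Dose 2 and post-Dose 3 summaries to subjects who received those doses. Within those groups, early leavers still count in full.

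A person-time estimate also brings assumptions of its own: non-informative censoring and, for a single rate, a roughly constant hazard. That is a reason to report it beside the crude percentage, not in its place.

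**Conclusion.** The point holds as a limited one. Whenever subjects leave inside the window and would have remained at some SAE risk, the primary SAE percentage falls below the full-window risk. The direction follows from the plan; the size cannot be derived from it. Under a constant hazard and even leaving, the relative shortfall is about q/2: 5% at an assumed 10% leaving and 15% at an assumed 30%. If withdrawals are as uncommon as the protocol expects, it is minor. No test, type I error rate or power figure is affected. The case for acting is that the correction is cheap, that the method is already in the SAP, and that current outputs do not show how complete the 6-month observation was.

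**What to change.** Change the SAP only. In 6.1.1.5, keep the crude percentage and add by cohort:
1. the number of subjects observed through 6 months after the last dose;
2. the rate of subjects with a first SAE per 100 person-years, with the exact Poisson interval from 5.2.2, or a Kaplan-Meier risk at the end of the window.

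End person-time at the earliest of first SAE, non-trial vaccination, withdrawal, loss to follow-up or end of the window. State the window end for Cohort 6 subjects who never receive Dose 3, because SAP 3.1.1 names Dose 3 as that cohort's last dose. State also that ending time at a non-trial vaccination describes risk in the absence of that vaccine.

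The cost is one table. Protocol 6.5.3 already requires dates for prohibited medications throughout participation, and discontinuation is recorded. The price in interpretation is the censoring assumption, which should be footnoted.

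No change to the schedule-of-activities notes or to Protocol 8.3.1 is proposed. SAP 8.3 records that an amendment was no longer possible and that the trial ended globally on 04 October 2023.
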